1.0 Aims

The goal of this study is to determine the extent to which standard care plus the Anticoagulation Choice tool promotes shared decision making (SDM) and impacts anticoagulation uptake and adherence versus standard care without this tool in patients with nonvalvular atrial fibrillation (AF).

Aim 1. To what extent does use of the ANTICOAGULATION CHOICE tool promote high-quality SDM versus standard care?

Using encounter video recordings and post-visit patient and clinician questionnaires, we will assess **SDM quality** (primary endpoint) **and processes**.

We hypothesize that use of the tool will improve SDM irrespective of patient literacy/numeracy, stroke risk, anticoagulation use at baseline, or type of clinic.

Aim 2. To describe the impact Anticoagulation Choice tool has on the rate of anticoagulation, the choice of anticoagulant, and adherence to anticoagulation in at-risk patients with AF versus the impact of standard care.

Using medical records and pharmacy profiles, we will determine the choice of anticoagulation, changes in anticoagulant use over time, and 12-month drug persistence, in all patients and in subgroups defined by patient literacy/numeracy, stroke risk, anticoagulation use at baseline, and type of clinic. As safety outcomes, we will monitor serious bleeding or strokes requiring medical attention.

2.0 Background and Significance

Atrial fibrillation is the most common cardiac arrhythmia affecting ~3 million Americans^{1,2} It accounts for ~\$26 billion/year in healthcare costs.³ AF-related thromboembolic strokes are often devastating and a cause of great physical, social and economic burden.⁴⁻⁷ Vitamin K

antagonists (VKAs, e.g., warfarin) reduce the risk of stroke by ~68%.⁸⁻¹³ Recently, non-VKAs oral anticoagulants (NOACs) that directly inhibit factor Xa (e.g., rivaroxaban, apixaban, edoxaban) or thrombin (dabigatran) have demonstrated similar to or better efficacy and safety than warfarin.¹⁴⁻¹⁶ Underuse of anticoagulation is a significant quality gap. Despite patients' strong aversion to strokes,^{17,18} <50% of high-risk patients with AF receive anticoagulants.¹⁹ Of these, 30-50% stop treatment within 12 months.²⁰⁻²³ The low rate of anticoagulation suggests that clinicians are challenged in initiating anticoagulation, in part due to clinicians' aversion to causing anticoagulation-related bleeding,^{19,24} Nonadherence suggests that some patients cannot implement anticoagulation in their lives: warfarin requires a stable diet and periodic laboratory (INR) monitoring,²⁵⁻²⁷ while NOACs are costly and lack bleeding reversal agents.¹⁴⁻¹⁶ Underuse may result also from poor patient and clinician access to, and deliberation with, individualized estimates of risks and benefits.^{28,29} Patients and clinicians require support in initiating and implementing anticoagulation therapy.

In 2014, three major cardiovascular organizations formulated guidelines for the management of patients with AF. They gave their strongest class I recommendation for using SDM to individualize anticoagulation in at-risk AF patients.³⁰ SDM has the potential to support patients and clinicians in collaborative deliberation about reasonable anticoagulation strategies matched to medical risk and patient circumstance.³⁰⁻³² Nevertheless, this recommendation is based on expert consensus (level C evidence) and translating it into practice is challenging. The guideline provides no guidance on how to achieve this, and no tools were available that are both up-to-date and proven to support SDM in this context. Furthermore, we do not know what effect SDM may have on anticoagulation rates and adherence in patients with AF.³⁰

We have developed and pilot tested a new online SDM tool (Anticoagulation Choice) to implement the 2014 class I recommendation in usual practice. The tool promotes a SDM conversation in the clinical encounter between the expert on important issues that bear on adherence, the patient, and the expert in medical issues, the clinician. Deliberating together on patient-important issues and medical matters, patients and clinicians can arrive at an evidence-based option that patients' value and can implement. Building on this experience,

we propose to implement SDM using the Anticoagulation Choice tool and evaluate its impact on SDM quality and on the rate by which patients take up anticoagulation and implement it in their lives.

3.0 Preliminary Work

[figure not shown]
The anticoagulation decision requires a conversation that discusses *both* the patient's risk of strokes and the issues that distinguish agents by fit with patient goals and situation. Using our user-centered design process, we created Anticoagulation Choice, a decision aid designed to support the recommendation for SDM for anticoagulation in AF. The development of the anticoagulation choice tool was built on 10 years of experience in designing decision aids that promote shared decision making and provide evidence-based content. The evidence-based content for this tool comes from systematic and expert reviews of randomized trials, observational studies, and qualitative studies.^{30, 33-42} Simultaneously, we conducted 16 direct observations in primary and specialty clinics of clinical encounters in which anticoagulation decisions took place. The goal of these observations was to identify areas of opportunity to improve extant conversations.⁴³ The first "low-fidelity prototype"⁴⁴ was a rough-draft paper version and was field-tested within 8 clinical encounters. Iterations followed, first on paper, and then electronically, seeking to achieve patient engagement in the conversation. We judged this to have taken place when patients asked questions or made statements considering how anticoagulation would play out in their daily lives. An electronic version was necessary to ensure risk tailoring for each patient and to facilitate updating (we designed the tool to accommodate new evidence and new agents) and distribution. The online version supports conversations with patients who are new to anticoagulation as well as former and current warfarin users. Its use in field-testing required minimal support. The baseline risk, tailored to the patient using the CHA₂DS₂-VASc score (a tool that estimates risk of stroke), is shown using words, numbers, and a 100-person pictograph along with the expected risk reduction with anticoagulation. If this benefit is compelling to the patient consideration moves on to the salient issues differentiating the available options. The issue cards include the risk of bleeding (based on HASBLED, a tool that estimates risk of bleeding), availability of reversal agents, and practical considerations. Practical considerations include how each

choice affects patients' ability to be active, to travel, to eat a variety of meals, how the medicine is taken and its effects monitored, and what are the out-of-pocket costs. The final version of the tool is focused on the discussion of these issues after considering the risk of stroke and the risk reduction with anticoagulation. The tool is web-based and will be integrated where possible with the electronic workflow.

4.0 Research Design & Methods

We will conduct a multicenter randomized trial at the patient level comparing the Anticoagulation Choice tool and standard care versus standard care alone where enrolled clinicians will administer the intervention among patients with nonvalvular AF deemed at high risk of thromboembolic strokes. The study will assess the impact of the interventions on SDM quality and impact on anticoagulation use as well as monitoring safety concerns of strokes and bleeds. Also, as part of this trial, clinician training sessions will be evaluated to describe the normalization process of anticoagulation decision aid in the clinical sites. Data collection will include medical record review, survey completion, and note taking or video/audio recording of the clinical encounter and training sessions.

4.1 Schema

4.2 Study Setting and Participation

The trial will take place in clinics at Mayo Clinic (academic medical center), Park Nicollet Health Partners (urban/suburban community medical center), Hennepin County Medical Center (safety-net inner-city medical center), UAB Medicine - The University of Alabama at

Birmingham and University of Mississippi Medical Center that treat patients with atrial fibrillation.

At each recruiting location designated site staff will be trained to review informed consent documents and obtain necessary signatures from patients and clinicians and will be observed doing so, by study personnel or research staff, prior to actually consenting patients or clinicians.

4.2.1 Eligibility Criteria for Clinicians

All clinicians (MDs, NP/PAs, PharmDs) that are responsible for the modality of Anticoagulation in eligible AF patients at participating sites, without exclusion.

4.2.1.1 Enrollment of Clinicians

The research team and site champions will present an overview of the study at a department meeting. The informed consent document will be reviewed with interested clinicians before the clinician receives training on using the decision aid at the initial recruitment meeting or at their convenience throughout the duration of the study, prior to their first enrolled patient. Study staff will observe the clinician trainings, described in 4.2.1.2. The clinician will have the option to consent to recordings (video/audio or audio only) of clinical encounters with enrolled patients. If the clinician declines to do the recording they are still eligible for participation within the study. If the clinician agrees to recording of the clinical encounters on the consent they can still decline at time of the clinical encounter.

The study coordinator will quickly setup and start recording before leaving the room. The participants can stop this recording (video, aimed at the desk, or audio when the video camera is aimed at the ceiling) at any time (the device has a large red start/stop button and an on/off indicator light).

Consent only needs to occur one time (prior to being trained to use the decision aid and prior to the visit with the first enrolled patient). There will be no monetary or other sort of

reimbursement for clinicians participating in the trial. The participation of clinicians as subjects will not affect their current or future employment or be shared with their supervisor.

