4.2.3 Identification of Subjects

Participants for all aims will be patients, their caregivers when pertinent, and clinicians. Participation is completely voluntary and we have procedures in place, sanctioned by the Mayo Clinic Institutional Review Board, Hennepin County Medical Center Institutional Review Board (HCMC), Park Nicollet Health Partners Institutional Review Board, UAB Medicine - The University of Alabama at Birmingham Institutional Review Board and University of Mississippi Medical Center Institutional Review Board to ensure that participants have the opportunity to opt out at any time and will not be further approached for participation or to provide data.

At the Mayo Clinic site, upcoming appointment lists for Atrial Fibrillation (AF) patients in primary care, cardiology, neurology, thrombophilia and anticoagulation clinics ECG result lists, medical records and clinician referrals will be reviewed for patient eligibility. Eligible patients will be approached and recruited in person, in a private location (i.e., clinic/exam room) prior to their appointment. Consent will occur by a trained research member as long as needed and until all questions by the subject have been answered. All study activities will occur within scheduled appointments, avoiding the need for additional research visits.

The patient and caregivers (if present), will be asked to provide consent to the recording (video/audio or audio only) of the clinical encounter. If the patient chooses to decline the recording they are still eligible to participate in the study. The study coordinator will quickly setup and start recording before leaving the room. The participants can stop this

recording (video, aimed at the desk, or audio when the video camera is aimed at the ceiling) at any time (the device has a large red start/stop button and an on/off indicator light).

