4.3 Registration and Randomization of Patients

Prior to registering patients to the study, all of the eligibility criteria on the eligibility checklist will have been met.

Patients will be randomized by the study coordinator after completion of standard informed consent for participation in clinical research including permission to use protected health information.

Registration/randomization is available via REDCap

 this is a secure, web-based application that is HIPPA compliant. Registration/randomization is available 24 hours a day via the REDCap website. Site staff will be provided a login and password by the study statistician.

Prior to accessing the REDCap website, site staff should verify the following:

- All eligibility criteria have been met.
- Informed consent has been obtained.
- Site staff has access to REDCap.

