4.5 Standard Care

The clinician will conduct the encounter per their standard of care. As access to the tool will be available to ensure contamination does not occur the study coordinator will inform the clinician prior to entering the room that the patient is to receive standard care and that the tool is not to be accessed.

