4.7.2 SDM processes

To assess SDM processes the recordings of the clinical encounter will be evaluated (video/audio or audio only recordings).

Extent of SDM that took place during the encounter will be assessing the degree of involvement of patients by the clinician in SDM using the OPTIONS scale.⁵³ The scale consists of 12 items scored from 0, no effort to 4, exemplary effort. The 12 items are summed and converted to a 100 point scale. A sample of 20% of the recordings will be assessed by two or more reviewers. Agreement will be assessed by Lin's concordance index⁵⁴, where any value over 0.8 will be considered concordant. If concordance does not occur within the first 20%, the two reviewers will assess cases of difference and review an additional 10 cases to test for agreement. Recordings scored by both reviewers will be averaged.

Impact of SDM on Encounter will be assessed by comparing the length in minutes of the discussion about anticoagulation and of the office visit, when available. Study coordinators when possible will time the encounters in intervention and control visits, prioritizing those encounters in which recording was not allowed. Potential issues preventing assessment of time may be recruitment of another patient.

Fidelity of SDM Tool by the clinician will be assessed by a review of the recording looking for key items to be addressed. A checklist of key elements will be assessed in both arms to assess not only the fidelity but potential contamination. A sum of the components in the checklist will be calculated for each recording and compared between arms. To score the recording first a sample of 20% of the video's will be assessed by two reviewers. Agreement will be assessed by Lin's concordance index⁵⁴, where any value over 0.8 will be considered concordant. If concordance does not occur within the first 20%, the two reviewers will assess cases of difference and review an additional 10 cases to test for agreement. Recordings scored by both reviewers will be averaged. For encounters where

audio and video recording has been declined, a real-time assessment will occur at the consent of the clinician and the patient. The study coordinator will conduct these real-time reviews.

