4.9.2 Sample Size Estimation

*The table shows the detectable effect for each of the outcomes of interest if we were to have data on that outcome from a total of 333 patients (1% of available population). This provides enough power ($\alpha=0.05$; two-sided difference) to detect meaningful differences across arms for all SDM quality and process outcomes. Our intent, however, is to have enough power to detect important differences when we conduct analyses of groups or cohorts of patients. Most of these analyses will divide the participants into 2 cohorts (e.g., start and review cohorts), except for the subgroup analysis by clinic, which divides the total sample into 3 cohorts: academic, community, and safety net clinic. That is the only analysis with three groups. Given this, we would need 3 times the sample size listed in the table, or **999 participants (3% of available sample)** to address all planned subgroup analyses. These are minimum targets for recruitment and we do not plan to limit recruitment in any way to enroll up*

to this number of patients. It assumes even distribution of participants per subgroup (e.g., start vs. review cohort); since the only grouping with three levels is clinic, each clinic will be expected to recruit similar numbers. Thus, for the main analysis and for other subgroup analyses (n=2 levels),

Outcome (n = 333)	Rate (%) or SD	Detectable effect	Power*
Patient level – SDM quality			
Knowledge transfer [^]	18	5.6	84%
Knowledge of risk	55%	15%	81%
Decisional conflict scale [^]	17	5.2	80%
Clinician level			
Satisfaction [^]	54%	15%	80%
Encounter level – SDM process			
Engagement (OPTION12) [^]	12.6	3.9	80%

[^] Values from iADAPT SDM tool trial; * $\alpha=0.05$; two-sided

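### A clinician who may already know the arm can decline recording, so OPTION12 may be compared in an arm-selected subset; the by-clinic OPTION12 power also allows for no unrecorded visits

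*Combined protocol and SAP*

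**What the plan says.** **Order of events.** Section 4.3: "Patients will be randomized by the study coordinator after completion of standard informed consent". Section 4.2.3 asks the patient about recording as part of consent, and a refusal does not exclude: "If the patient chooses to decline the recording they are still eligible to participate in the study". So the patient's initial choice comes before allocation.

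**Clinician.** Section 4.2.1.1 takes a general recording choice at one-time clinician consent, then adds: "If the clinician agrees to recording of the clinical encounters on the consent they can still decline at time of the clinical encounter". Once the camera runs, "The participants can stop this recording (video, aimed at the desk, or audio when the video camera is aimed at the ceiling) at any time".

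**Disclosure of the arm.** Section 4.5, to prevent contamination: "the study coordinator will inform the clinician prior to entering the room that the patient is to receive standard care". Section 4.4 does not describe the matching step for the tool arm, but the clinician has to know in order to use the tool.

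**Outcome.** Section 4.7.2: "To assess SDM processes the recordings of the clinical encounter will be evaluated". OPTION12 is one of these process outcomes. The same section provides a substitute for unrecorded visits, but only in the fidelity paragraph: where "audio and video recording has been declined, a real-time assessment will occur at the consent of the clinician and the patient". Coordinators also time visits where possible, giving priority to unrecorded ones. No substitute is written for OPTION12.

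**Sample size.** Section 4.9.2 gives 80% power for OPTION12 (SD 12.6, detectable difference 3.9) "if we were to have data on that outcome from a total of 333 patients". It then triples 333 to 999 so that all planned subgroup analyses, including the three clinic types, are covered.

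**The concern.** Section 4.9.1 counts SDM processes, together with SDM quality, among the main analyses. For OPTION12, the clinician whose conversation is being rated can decide, possibly knowing the arm, whether a rating will exist. If refusals differ by arm and are related to how the conversation would have gone, the recorded visits in the two arms are no longer comparable, and randomization does not protect the contrast. The direction could go either way: a clinician might be less willing to be filmed without the tool, or less willing while using an unfamiliar one.

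The second matter is smaller. The target of 999 treats every enrolled patient as a patient with OPTION12 data. Section 4.9.2 does reduce the number for pharmacy records (about 90% on treatment, more than 85% of records obtained, about 765 of 999), so the plan recognises this kind of loss for one outcome and not for the other.

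**Working it through.** **1. Can refusal follow disclosure?** Set the sections side by side:

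| Step | Section | Before or after randomization |
|---|---|---|
| Clinician's general recording consent | 4.2.1.1 | Before (once, ahead of the first patient) |
| Patient's recording decision | 4.2.3 | Before (at consent) |
| Randomization | 4.3 | – |
| Clinician told the visit is standard care | 4.5 | After |
| Clinician may decline for this visit | 4.2.1.1 | At the encounter; order relative to disclosure not fixed |
| Anyone may stop recording | 4.2.1.1, 4.2.3 | After |

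A clinician who refuses recording altogether does so before any allocation. With patient-level randomization, that removes visits from both arms alike. The exposed steps are the clinician's per-visit refusal and later stopping.

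**2. How large might the bias be? (illustration; all inputs assumed except the SD of 12.6)** Suppose one arm loses 20% of its recordings and the other none, and willingness to be recorded correlates r with the OPTION12 score under a normal selection model. The mean of a standard normal variable above its 20th percentile is φ(0.84)/0.80 = 0.280/0.80 = 0.35. The shift in that arm's mean is r × 12.6 × 0.35:

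- r = 0.3: 1.3 points, one third of the 3.9-point detectable difference
- r = 0.5: 2.2 points
- r = 0: none

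**3. Reproduce the stated power.** Inputs from section 4.9.2: difference 3.9, SD 12.6, two-sided alpha 0.05, 333 with data. Assumed: 1:1 allocation (no ratio is stated) and no clinician clustering.

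Power = Φ(3.9 / (12.6 × √(4/n)) − 1.96). With n = 333: 12.6 × √(4/333) = 1.381; 3.9/1.381 = 2.824; Φ(0.864) = 80.6% (80.4% by noncentral t). The stated 80% reproduces. The smallest n giving 80% is 328.

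**4. Vary the recording rate.** The documents give none, so a range is assumed, equal in both arms and, for the by-clinic column, with 333 enrolled per clinic type (n left unrounded):

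| Recorded | n per clinic type | Power | n overall | Power |
|---|---|---|---|---|
| 100% | 333 | 80.6% | 999 | 99.8% |
| 90% | 299.7 | 76.4% | 899.1 | 99.6% |
| 80% | 266.4 | 71.4% | 799.2 | 99.2% |
| 70% | 233.1 | 65.6% | 699.3 | 98.4% |
| 50% | 166.5 | 51.5% | 499.5 | 93.3% |
| 33.3% | 111 | 37.1% | 333 | 80.6% |

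Recording rate at which power reaches 80%: overall 328/999 = 33%; two equal subgroups 328/499.5 = 66%; three clinic types 328/333 = 98.5%.

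Unequal recording of 80% and 60% by arm gives 98.2% overall and 64.8% per clinic type. Unequal loss therefore costs the overall comparison little power; what matters there is the possible bias.

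**The case against.** **The text does not say that refusal follows disclosure.** True. Sections 4.2.1.1 and 4.5 leave the order of the two steps open, so arm-dependent refusal is a possibility and not a documented event. But the plan does not exclude it either, and refusal at the encounter sits naturally at or after the moment when the clinician is told.

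**Safeguards exist.** Section 4.9.1.1 promises missing-data rates by outcome and arm, which for OPTION12 amounts to the recording rate. Section 4.9.1 promises imputation. The first stands and makes part of any remedy unnecessary. It reveals an imbalance but does not prevent one. The second refers to section 4.9.1.1, which names no method, and standard imputation does not repair refusal that depends on the unobserved quality of the conversation.

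**Not all process outcomes are affected alike.** Accepted. Fidelity has a real-time substitute (itself subject to consent) and visit length can be timed by the coordinator. The point is about OPTION12.

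**Power.** A reader might infer that missing recordings make the stated 80% wrong, or leave the main OPTION12 comparison underpowered. The documents support neither. The 80% is conditional on 333 patients with data, and the overall comparison has three times that number enrolled. 999 is also a minimum and not a cap. The shortfall is confined to the by-clinic analysis, which section 4.9.1 calls descriptive. That limits its weight, but section 4.9.2 still offers 999 as enough for all planned subgroup analyses.

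**Patients.** A reader might also infer that patient refusals are arm-dependent. Sections 4.2.3 and 4.3 put the patient's initial decision before randomization; only later stopping is exposed.

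**Conclusion.** The plan leaves open a route by which OPTION12 data can be missing according to arm: the clinician's per-visit refusal, made with possible knowledge of the allocation, and stopping during the visit. Whether this happens, how often and in which direction cannot be told from the documents. Under the assumed selection model a shift of 1.3 to 2.2 points is conceivable against a detectable 3.9, and none if refusal is unrelated to the score. Section 1.0 names SDM quality as the primary endpoint, so the exposed outcome is a main analysis but not the primary one.

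The power point holds only for OPTION12 by clinic type, where power drops below 80% once fewer than about 98.5% of visits are recorded. These powers rest on 1:1 allocation, three clinic types of equal size and no clustering by clinician; clustering would lower all of them. The point warrants a change because the remedy costs almost nothing.

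**What to change.** 1. In sections 4.2.1.1 and 4.5, fix the order of steps: the coordinator asks for and logs the clinician's recording decision for that visit, and only then discloses the arm. This applies to both arms. Everyone keeps the right to stop recording at any time.
2. Log the reason for each unrecorded or stopped visit and report the reasons by arm, next to the missing-data rates already promised in section 4.9.1.1.
3. In section 4.9.2, state the expected recording rate and give the by-clinic OPTION12 power for the number then expected to have data. Enrolment does not need to change.

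Cost: a small change in the coordinator's sequence, one more logged item, and a less favourable subgroup power on paper. No extra patients or staff are needed. Stopping after disclosure remains possible and may still depend on arm; the change narrows the route but cannot close it, which is why the stopping log matters.
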